2.2 Rationale

 
2.4 Risk: Benefit Assessment
2.7 Misk. Denent Assessment

3. Study Objectives and Endpoints

3.1 Primary objective and primary efficacy endpoint

Primary objective	Primary efficacy endpoint
To evaluate the efficacy of SHR0302 4 mg QD, 8 mg QD compared to placebo in adult subjects with moderate to severe atopic dermatitis at Week 12	• The percentage of subjects achieving IGA response at Week 12. IGA responsed is defined as IGA 0/1 (clear/almost clear) together with IGA improvement ≥ 2 from baseline

3.2 Secondary objectives and Secondary Endpoints

Secondary objectives	Secondary endpoints
To evaluate safety and tolerability of oral SHR0302 in subjects with moderate to severe atopic dermatitis	To assess safety and tolerability by laboratory parameters
	To assess safety and tolerability by collection of AE/SAE incidence
	To measure vital signs (blood pressure, heart rate, body temperature and respiratory rate)
	To measure subjects' total lipid profile, including triglycerides, low-density lipoprotein (LDL), and high-density lipoprotein (HDL)
	• To measure subjects' thyroid profile: TSH, free T4 and free T3
	To evaluate liver and renal function
	• 12-lead ECG
To evaluate the other efficacy endpoint and patient reported outcome of SHR0302 in adult subjects with moderate to severe	• Percentage of EASI change from baseline at Weeks 1, 4, 8, and 12
atopic dermatitis	 Percentage of Subjects Achieving IGA Response at Weeks 1, 4, 8
	• Percentage of Subjects With ≥ 50%, 75%, and 90% EASI improvement from baseline (EASI50, EASI75, EASI90) at Weeks 1, 4, 8, and 12
	• Mean change from baseline in SCORAD at Weeks 1, 4, 8, and 12
	 Percentage of Subjects With ≥ 50%, 75%, and 90% SCORAD improvement from baseline (SCORAD50, SCORAD75, SCORAD90) at Weeks 1, 4, 8, and 12

Secondary objectives	Secondary endpoints
	• Percent of pruritus numerical rating scale (NRS) change from baseline at Weeks 1, 4, 8, and 12
	• Percentage of Subjects Achieving Pruritus NRS improvement ≥3 from Baseline in at Weeks 1, 4, 8, and 12
	• Change from baseline in Dermatology Life Quality Index (DLQI) at Weeks 1, 4, 8, and 12
	• Change from baseline in biomarker IgE at weeks 1, 4, 8 and 12
To explore Pharmacokinetic and dose- response properties of SHR0302 in subjects with moderate to severe atopic dermatitis.	Systemic exposure of SHR0302 at steady state in subjects with atopic dermatitis (ie: concentration and area under the curve)

4. Investigational Plan

4.1 Study Design

See Figure 1.

[figure not shown]

Figure 1. Study Design Diagram

4.2 Discussion of the design

This is a randomized, double-blind, placebo-controlled, multicenter phase II study that will enroll 132 subjects with moderate to severe atopic dermatitis. This study consists of a 4-week screening period followed by a 12-week blinded treatment period and 2-week follow-up after last dose. At baseline visit, subjects with moderate to severe atopic dermatitis who meet all inclusion criteria/do not meet any of the exclusion criteria will be randomized in a 1: 1: 1 ratio during the treatment period to one of 3 study groups (2 active drug dose groups (4 mg QD, 8 mg QD) and placebo group).

All subjects will be followed-up for further 2 weeks until Week 14 (Final Visit). Subjects who withdraw early will be followed for an additional 2 weeks.

The end of study is defined as the date of last subject's last visit or actual date of follow-up, whichever is later.

5. Subject Selection and Withdrawal Criteria

5.1 Number of Subjects

132 eligible subjects will undergo randomization to achieve the estimated evaluable subjects in the study. The following criteria are designed to select subjects suitable for treatment according to the protocol. All relevant medical and non-medical conditions should be considered when deciding whether a subject is suitable for participation in this study. Subjects' eligibility should be reviewed and documented by a qualified appropriate member of the investigator's study team prior to subject enrollment in the study. Subjects must be able to voluntarily provide informed consent for participation in this study.

5.2 Inclusion criteria

Subjects must meet all the following inclusion criteria to be eligible for enrollment into the study:

- 1. Subjects between 18-75 years of age (inclusive), male or female, at the time of informed consent
- 2. Moderate to severe atopic dermatitis, as determined by all of the following:
 - Have a clinical diagnosis of AD for at least 1 year before Visit 1 (Chinese Criteria of AD refer to Appendix 1)
 - \circ EASI \geq 12, BSA \geq 10%, and IGA \geq 3 at the Screening and Baseline Visits
 - o In the judgment of the investigator, subjects who have inadequate response and/or cannot be tolerable, to one or more of the below treatments for at least 4 weeks
 - Topical therapy (topical corticosteroids and/or topical calcineurin inhibitors)
 - Systemic steroids and/or phototherapy

- Cyclosporine and/or other immunomodulators (e.g., methotrexate, mycophenolate mofetil, and azathioprine, etc.)
- 3. Capable of providing a signed and dated informed consent form indicating the subject has been informed of all pertinent aspect of the study
- 4. All women of childbearing potential and all men must be willing to use at least one highly effective method of contraception from signing of informed consent, throughout the duration of the study, and for 1 month after last dose of study medication: (refer to Section 5.4 for further details on contraception requirements for this study)
 - o Male subjects with a female partner of childbearing potential must be willing to use condom in addition to a highly effective contraceptive method.
- 5. Subjects who are willing and able to comply with the scheduled visits and treatment plan, laboratory testing and other study procedure
- 6. Subjects receiving non-prohibited concomitant medications for any reason must maintain a stable dosing regimen, defined as no administration of a new drug or no change in dose within 7 days or 5 half-lives (whichever is longer) prior to the first dose of study drug

5.3 Exclusion Criteria

Subjects presenting with any of the following criteria will not be enrolled in this study:

- 1. Subjects with historical or current evidence of clinically significant cardiovascular, neurological, psychiatric, renal, hepatic, immunological, gastrointestinal, urogenital, nervous system, musculoskeletal, skin, sensory, endocrine (including uncontrolled diabetes or thyroid disease) or hematological abnormalities that are uncontrolled. Significant is defined as any disease that, in the opinion of the Investigator, would put the safety of the subject at risk through participation, or which would affect the efficacy or safety analysis if the disease/condition exacerbated during the study
- 2. Subject has a current diagnosis of other active skin disease (e.g., psoriasis or lupus erythematosus) or skin infection (bacterial, fungal, or viral) that may affect the evaluation of atopic dermatitis
- 3. Subject has a severe comorbidity that may require systemic steroids therapy or other interventions or requires active frequent monitoring (e.g., unstable chronic asthma)
- 4. Subjects with evidence of hematopoietic disorders:
 - o Hemoglobin level < 9.0 g/dL or hematocrit < 30% at screening visit or within 3 months prior to baseline
 - Absolute white blood cell (WBC) count <3.0 x 10⁹/L (<3000/mm³) or Absolute Neutrophil Count (ANC) of <1.2 X 10⁹/L (<1200/mm³) at screening visit or within the 3 months prior to baseline.

- o Thrombocytopenia, as defined by a platelet count $<100 \times 10^9/L$ ($<100,000/mm^3$) at screening visit or within the 3 months prior to baseline.
- 5. Subjects with evidence of total bilirubin, aspartate aminotransferase (AST) or alanine aminotransferase (ALT) more than 2 times the upper limit of normal at screening visit. Patients with liver cirrhosis will be excluded.
- 6. Subjects with eGFR \leq 60 ml/min based on Cockcroft-Gault calculation (Appendix2), or patients currently undergoes regular hemodialysis
- 7. Subjects with current clinically significant infections or within 6 months of baseline (e.g., those requiring hospitalization or parenteral antimicrobial therapy or opportunistic infections), or those with a history of more than one episode of herpes zoster, a history (single episode) of disseminated zoster, a history of any infection otherwise judged by the investigator to have the potential for exacerbation by participation in the study
- 8. Subjects may have evidence of active, latent, or inadequately treated infection with Mycobacterium tuberculosis (i.e., tuberculosis [TB]), as defined by the following:
 - Negative QuantiFERON TB Gold (QFT Gold test) /or T-Spot test performed within the 3 months prior to/within screening;
 OR
 - Subjects have a chest radiograph, taken within the 3 months prior to/within screening, and showing no change suggestive of active TB infection
 OR
 - Subjects have history of either untreated or inadequately treated latent or active TB infection
- 9. Subjects have received systemic corticosteroids, cyclosporin or other immunosuppressants (e.g., methotrexate, mycophenolate mofetil and azathioprine) or PDE4 inhibitor or phototherapy (e.g., UVB) treatment within 4 weeks of first dose of study drug
- 10. Subjects have received topical treatment (which may affect AD, e.g., topical corticosteroids, topical calcineurin inhibitor, antibiotic compound cream and topical herbal) within 2 weeks of firs dose of study drug
- 11. Subjects who may have current immunization with any live virus vaccine or history of immunization with any live virus vaccine within 8 weeks of baseline
- 12. Women who are pregnant or lactating or planning pregnancy while enrolled in the study
- 13. History of alcohol or drug abuse with less than 6 months of abstinence prior to baseline
- 14. Screening 12-lead ECG that demonstrates clinically relevant abnormalities which may affect subject safety if being enrolled into the study or interpretation of study results. (Appendix 3 ECG Exclusion Criteria)
- 15. Subjects with temperature \geq 38 ° C at screening or baseline
- 16. Subjects with malignancies or a history of malignancies except for adequately treated or excised non-metastatic basal cell or squamous cell carcinoma of the skin

- 17. Subjects with positive human immunodeficiency virus (HIV) or hepatitis B virus or hepatitis C virus-related laboratory tests
- 18. Subjects who currently have thyroid disorders (including hyperthyroidism, hypothyroidism, or are currently receiving thyroid replacement therapy. Subjects with abnormal TSH, fT4, and fT3 values on blood tests at screening must be excluded
- 19. Subjects who have previously been treated with JAK inhibitors (for example: tofacitinib, baricitinib, upadacitinib, PF04965842, etc.)
- 20. Subjects who have previously been treated with biologics (Dupilumab, etc.)
- 21. Subjects receiving or are expected to receive prohibited concomitant medication(s) within 4 weeks prior to the first dose of study drug (see Appendix 4)
- 22. Subjects who have received herbal treatment of unknown nature or known efficacy within 4 weeks prior to the first dose of study drug
- 23. Subjects who, in the opinion of the investigator, will be uncooperative or unable to comply with the study procedures
- 24. Any other condition which in the opinion of the investigator would make the subject unsuitable for inclusion in the study.

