5.5 Randomization Criteria

At randomization visit (Visit 2), subjects who meet all inclusion criteria and do not meet any exclusion criteria will be randomized in a 1: 1: 1 allocation ratio to SHR0302 4 mg QD, SHR0302 8 mg QD, or placebo. Subjects will be assigned to treatment groups using a computer-generated randomization table. Subjects will be assigned subject numbers in the order in which they consent to participate in the study. This identification number will be kept throughout the study.

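### Exclusion criterion 8 is inverted: as written, a negative TB test or a clear chest film excludes a subject, and a positive test does not in itself exclude

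*Protocol*

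**What the plan says.** Protocol 5.3 opens with the operator for the whole list: "Subjects presenting with any of the following criteria will not be enrolled in this study". Section 5.5 applies it at Visit 2, where "subjects who meet all inclusion criteria and do not meet any exclusion criteria will be randomized".

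Item 8 is headed "Subjects may have evidence of active, latent, or inadequately treated infection with Mycobacterium tuberculosis (i.e., tuberculosis [TB]), as defined by the following". Three bullets, joined by OR, supply the definition:

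- Bullet 1: "Negative QuantiFERON TB Gold (QFT Gold test) /or T-Spot test performed within the 3 months prior to/within screening".
- Bullet 2: a chest radiograph from the same period, "showing no change suggestive of active TB infection".
- Bullet 3: "Subjects have history of either untreated or inadequately treated latent or active TB infection".

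Elsewhere, Table 1 (5.11) schedules the assay at Screening, and a chest X-ray there unless an X-ray or CT from the previous 3 months is available. Sections 7.3.3 (QuantiFERON) and 7.3.5 (T-SPOT.TB) explain how the assays work and leave the choice between them to the investigator. SAP 13.3 lists the TB test among the baseline summaries. None of these says what a positive result means for eligibility.

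**The concern.** The heading announces evidence of TB, and two of the three conditions that define it are evidence against TB. A site that follows the bullets excludes every subject with a negative assay or a clear film, which is the population the trial means to enroll. A positive assay is not a ground for exclusion under any bullet.

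This is an eligibility and safety matter. Study drug is an oral JAK1 inhibitor. The plan itself treats infection as an important risk: a serious infection forces discontinuation (Protocol 5.6) and is an adverse event of special interest (SAP 15.2.5). Safety review rests with the sponsor's study team (Protocol 10.7). Screening is the one TB safeguard that acts before exposure.

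It also affects deviation reporting. SAP 13.2 counts breaches of the inclusion and exclusion criteria among major protocol deviations. Judged by the text, every intended enrollee breaches item 8, and a subject with both a positive assay and a suggestive film does not.

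**Working it through.** The plan gives no figure to reproduce here. The check is one of logic.

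**Inputs.** Three binary conditions from item 8: assay (negative or positive), film (clear or suggestive of active TB), and history of untreated or inadequately treated TB (no or yes). That gives 2 × 2 × 2 = 8 profiles.

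**Rules compared.**

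- A, as written: exclude if assay negative OR film clear OR history.
- B, bullets 1 and 2 reversed to match the heading: exclude if assay positive OR film suggestive OR history.
- C, bullets 1 and 2 read as misplaced inclusion conditions with the OR kept: eligible if (assay negative OR film clear) AND no history.
- D, as C but joined by AND: eligible if assay negative AND film clear AND no history.

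| Assay | Film | History | A | B | C | D |
|---|---|---|---|---|---|---|
| negative | clear | no | out | **in** | **in** | **in** |
| negative | clear | yes | out | out | out | out |
| negative | suggestive | no | out | out | **in** | out |
| negative | suggestive | yes | out | out | out | out |
| positive | clear | no | out | out | **in** | out |
| positive | clear | yes | out | out | out | out |
| positive | suggestive | no | **in** | out | out | out |
| positive | suggestive | yes | out | out | out | out |
| Eligible | | | 1 of 8 | 1 of 8 | 3 of 8 | 1 of 8 |

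**Results.**

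1. A and B disagree on exactly two profiles. The subject with no sign of TB is barred under A, and the subject with both signals passes.
2. Under A, an assay-positive subject is still excluded if the film is clear (bullet 2) or there is a qualifying history (bullet 3), but never because of the assay.
3. B and D are the same rule. C is not: it admits a positive assay with a clear film, although the heading names latent infection, and it admits a negative assay with a suggestive film. Two natural repairs of the same text therefore give different eligible populations.

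**Whether another rule supplies the answer.** Item 17 excludes on positive HIV, hepatitis B or hepatitis C tests; TB has no counterpart. Item 7 covers clinically significant infection and "a history of any infection otherwise judged by the investigator to have the potential for exacerbation by participation in the study". Item 24 covers "Any other condition which in the opinion of the investigator would make the subject unsuitable for inclusion in the study". Either could catch the profile that passes A, but both depend on judgement and neither names TB or a positive assay.

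**The case against.** The strongest reply is that the heading makes the intent plain. A positive assay is naturally evidence of latent infection, no investigator would treat a negative test as evidence of TB, and a site applying the bullets could not enroll its ordinary patients and would raise a query at once. This stands as a forecast of behavior: most sites would probably screen out positive assays. It does not settle the rule, because rules B and C are both plausible corrections and differ on whether an assay-positive subject with a clear film may enter.

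The profile that passes may also be narrower than the table suggests. A never-treated subject with a positive assay and a suggestive film might be said to meet bullet 3, if history includes a new finding, and item 7 excludes current clinically significant infection. Both are fair points, but the first depends on how a word is read and the second on what counts as clinically significant.

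The eight profiles are logical cells, not subjects. The documents give no TB prevalence, so the count says nothing about how many subjects would be wrongly enrolled, and indeterminate assay results are left out. That is correct, and the count is used here only to show what each rule does.

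Finally, a flat rule that any positive assay excludes might bar subjects with adequately treated TB, for whom bullet 3 appears to leave room. That is a clinical choice for the sponsor to make in the corrected text.

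**Conclusion.** Item 8 is wrong as written and must be corrected. Two of its three bullets have the opposite sense to the heading. Followed as it stands, the criterion bars the intended enrollee, passes only the subject with positive assay, suggestive film and no untreated or inadequately treated history, and never excludes on a positive assay alone.

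The conclusion assumes that the bullets define the criterion, as the heading says they do, and that each assay or film result falls into one of two classes. It does not assume that anyone was wrongly enrolled. Nothing in the sample size, the type I error control or the full analysis set analysis of the primary endpoint changes. The severity rests on subject safety and on an eligibility rule that can be neither followed nor audited.

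**What to change.** Reword item 8 to exclude a subject with any of the following:

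- a positive QuantiFERON or T-Spot result, in the 3 months before screening or during it;
- a chest radiograph in the same window with changes suggestive of active TB;
- a history of untreated or inadequately treated latent or active TB.

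Alternatively, require a negative assay AND a clear film AND no such history as an inclusion criterion. If bullets 1 and 2 are moved to the inclusion list, the OR between them must become AND; otherwise the result is rule C, with 3 of 8 profiles eligible.

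The sponsor's clinical team should state in the same text how a positive assay with a clear film, and a positive assay after adequate treatment, are handled.

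The cost is a protocol wording amendment and a notice to sites. No procedure is added, since Table 1 already provides for the assay and chest imaging at Screening.

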5.4 Contraception advice

Contraceptive measures for both male and female subjects with childbearing potential should be documented in the original document.

5.4.1 Female subjects of non-Childbearing potential

Female subjects of non-childbearing potential must meet at least one of the following criteria:

Postmenopausal female who are at least 45 years of age with amenorrhea for at least 2 years.
 To confirm the postmenopausal status (FSH level > 30 IU/L), FSH testing should be performed for women within 5 years from their last menses;

OR

 Female subjects with physician documented hysterectomy, bilateral salpingectomy and/or bilateral oophorectomy

All other female subjects (including women with tubal ligations) will be considered as of childbearing potential.

5.4.2 Female subjects with childbearing potential

Female subjects with childbearing potential and their male partners must use at least one of the following highly effective methods of contraception:

a. Combined (oestrogen and progestogen containing) hormonal contraception associated with inhibition of ovulation (oral, intravaginal, or transdermal).

- b. Progestogen-only hormonal contraception associated with inhibition of ovulation (oral, injectable, or implantable).
- c. Placement of an intrauterine device (IUD) or intrauterine hormone-releasing system (IUS)
- d. Documented bilateral tube occlusion at least 4 weeks before screening
- e. Vasectomized partner with medical confirmation of absence of sperm in the ejaculate at least 4 weeks before screening.

Female subjects and their heterosexual partners must be willing to continue use of these contraceptive methods from signing of informed consent, throughout the duration of the study, and for 1 month after last dose of study medication. Within these limits, the specific forms of contraception employed are left to the discretion of the subject, the principal investigator, and/or the subject's physician.

Absolute sexual abstinence, when this is consistent with the preferred and usual lifestyle of the subject, may be considered an acceptable method of contraception at the discretion of the investigator.

5.4.3 Pregnancy tests

Female subjects of childbearing potential will be tested for serum beta-human chorionic gonadotropin (β -hCG) at screening visit. In addition, urine β -hCG test will be done at baseline and at each study visit until the end of follow-up period. If at any point there is a case of a positive urine β -hCG test, and this is confirmed by serum β -hCG, the subject will be withdrawn from the study and all the necessary follow up will be conducted.

5.4.4 Males

Non-vasectomized males with female partners of childbearing potential must be willing to use a condom, from signing of informed consent, throughout the duration of the study, and for 1 month after last dose of study medication, in addition to having their female partner use a highly effective form of contraception as described in Section 5.4.2.

Vasectomized males with female partners of childbearing potential are not required to use an additional form of contraception providing that surgical sterilization has been successful and an absence of sperm in the ejaculate has been confirmed at least 4 weeks before screening.

5.5 Randomization Criteria

At randomization visit (Visit 2), subjects who meet all inclusion criteria and do not meet any exclusion criteria will be randomized in a 1: 1: 1 allocation ratio to SHR0302 4 mg QD, SHR0302 8 mg QD, or placebo. Subjects will be assigned to treatment groups using a computer-generated randomization table. Subjects will be assigned subject numbers in the order in which they consent to participate in the study. This identification number will be kept throughout the study.

